**Clinical Investigational Plan**

	meet termination criteria (x)	
20	6	0.0251
30	8	0.0211
40	9	0.0423

If the Sponsor suspends or prematurely terminates the clinical investigation at an individual investigational site in the interest of safety, the Sponsor will inform all other Principal Investigators.

If suspension or premature termination occurs, the Sponsor will remain responsible for providing resources to fulfill the obligations from the CIP and existing agreements for following up the subjects enrolled in the clinical investigation, and the Principal Investigator or authorized designee will promptly inform the enrolled subjects at his/her investigational site, if appropriate.

**14.1 Study Conclusion**

The study will be concluded when:

1. All sites are closed AND
2. The final report generated by Abbott has been provided to sites or Abbott has provided formal documentation of study closure

**15.0 Publication Policy**

The results of the clinical study will be submitted, whether positive or negative for publication.

A 'Publication Agreement' will be signed between the Principal Investigator and the Sponsor either as a separate Publication Agreement or within the Clinical Trial Agreement.

For more information on publication guidelines, please refer to the International Committee of Medical Journal Editors (ICMJE) on [www.icmje.org](http://www.icmje.org).

This study will be posted on ClinicalTrials.gov and results will be posted on ClinicalTrials.gov as required.

## Clinical Investigational Plan

### Appendix A: Abbreviations

Select or add abbreviations used

Abbreviation	Term
ADE	Adverse Device Effect
AE	Adverse Event
ASADE	Anticipated Serious Adverse Device Effect
CA	Competent Authority
CEC	Clinical Events Committee
CIP	Clinical Investigational Plan
CRF	Case Report Form
DD	Device Deficiency
DMP	Data Management Plan
EC	Ethics Committee
ECG	Electrocardiogram
eCRF	Electronic Case Report Form
EDC	Electronic Data Capture
EMEA	Europe, Middle East, Africa
IB	Investigator Brochure
ICMJE	International Committee of Medical Journal Editors
ISO	International Organization for Standardization
MP	Monitoring Plan
NA	Not Applicable
PI	Principal Investigator
RDC	Remote Data Capture
SADE	Serious Adverse Device Effect
SAE	Serious Adverse Event
SJM	St. Jude Medical
USADE	Unanticipated Serious Adverse Device Effect
WMA	World Medical Association

**Clinical Investigational Plan****Appendix B: CIP Revision History****Procedure for CIP Amendments**

This CIP may be amended as appropriate by the Sponsor. Rationale will be included with each amended version in the revision history table below. The version number and date of amendments will be documented.

The acknowledgement of the amended CIP by the Steering Committee Co-chairs and the Principal Investigators will be collected on the signature pages.

EC and relevant Regulatory Authorities, if applicable, will approve all amendments to the CIP.

Revision History				
Amendment Number	Version	Date	Rationale	Details
Not Applicable	VA	22 Sep 2016	First release of CIP	NA
	VB	2 Feb 2017	Requested updates from Competent Authority	
	VB	3 Mar 2017	Requested updates from Competent Authority	
	VC (Switzerland only)	31 May 2017	Requested updates from Competent Authority	
	VC (Switzerland only)	22 Jun 2017	Requested updates from Competent Authority	

**Clinical Investigational Plan****Appendix D: Definitions**

Cardiovascular Mortality (VARC2)	
Any 1 of the following criteria:
 
 
• Death due to proximate cardiac cause (e.g., myocardial infarction, cardiac tamponade, worsening heart failure)
 
• Death caused by non-coronary vascular conditions such as neurological events, pulmonary embolism, ruptured aortic aneurysm, dissecting aneurysm, or other vascular disease
 
• All procedure-related deaths, including those related to a complication of the procedure or treatment for a complication of the procedure
 
• All valve-related deaths including structural or nonstructural valve dysfunction or other valve-related adverse events
 
• Sudden or unwitnessed death
 
• Death of unknown cause
 

Myocardial Infarction (VARC2)	
POST TAVI Definition (VARC2)
 
Periprocedural MI (less than or equal to (<math>\leq</math>) 72 h after the index procedure)
 
New ischemic symptoms (eg, chest pain or shortness of breath), or new ischemic signs (eg, ventricular arrhythmias, new or worsening heart failure, new ST-segment changes, hemodynamic instability, or imaging evidence of new loss of viable myocardium or new wall motion abnormality),
 
AND
 
Elevated cardiac biomarkers within 72 h after the index procedure consisting of at least 1 sample postprocedure with a peak value exceeding 15x upper reference limit (troponin) or 5x for CK-MB. If cardiac biomarkers are increased at baseline (<math>>99^{\text{th}}</math> percentile), a further increase of at least 50% postprocedure is required AND the peak value must exceed the previously stated limit.
 
Spontaneous MI (greater than 72 h after the index procedure)
 
Any 1 of the following criteria:
 
 
• Detection of rise and/or fall of cardiac biomarkers (preferably troponin) with at least 1 value above the 99th percentile URL, together with evidence of myocardial ischemia with at least 1 of the following: 
 
○ Symptoms of ischaemia
 
○ ECG changes indicative of new ischemia [new ST-T changes or new Left Bundle Branch Block]
 
○ New pathological Q waves in at least 2 contiguous leads
 
○ Imaging evidence of new loss of viable myocardium or new wall motion abnormality
 
 
 
• Sudden, unexpected cardiac death, involving cardiac arrest, often with symptoms suggestive of myocardial ischemia, and accompanied by presumably new ST-segment elevation, or new LBBB, and/or evidence of fresh thrombus by coronary angiography and/ or at autopsy, but death occurring before blood samples could be obtained, or at a time before the appearance of cardiac biomarkers in the blood.
 
• Pathological findings of an acute myocardial infarction.
 

Stroke (FDA/VARC2)	
This study is following the FDA's definition of Stroke per FDA's Current Thinking Regarding Neurological Assessments for Transcatheter aortic valve Trials (Revised: 25 Aug 2011).

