### 5.4 Study Activities

Table 2. Study Activity Definitions

Study Activity Definitions	
Study Activity	Definition
Adverse Event Assessment	Adverse events will be documented according to definitions in Appendix D.
Barthel Index	A scale used to measure performance in activities of daily living (ADL). Each performance item is rated on this scale with a given number of points assigned to each level or ranking. It uses ten variables describing ADL and mobility where a higher number is associated with a greater likelihood of being able to live at home with a degree of independence following discharge from the hospital.
Blood Work	Blood lab tests will be collected at each required interval. The specific lab tests are indicted in Table 4
Cardiac Rhythm Monitoring	Assessment of heart rate, QRS and dominant rhythm preprocedure and during the procedure.
Chest X-Ray	Imaging conducted at Baseline per institutional guidelines.
Coronary and Aortic Angiogram with Runoff	Angiographic imaging off aortic arch the coronary, subclavian and axillary arteries. Assessment to be conducted per institutional guidelines.
CT Scan	Assessment to be conducted per institutional guidelines.
Echocardiography	Each site is responsible for performing the echocardiogram (echo) according to the Echocardiographic protocol. Echocardiogram will be copied to CD/DVD (or other large media storage device) and provided to an Echocardiographic Core Lab for evaluation.
Electrocardiogram (ECG)	Assessment of dominant rhythm, heart rate, and QRS interval via 12-lead.

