**5.7.3 Post Procedure Activities**

1. Blood work (within 48 hours post implant, refer to Table 4)
  - Creatinine
  - Urea

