## Clinical Investigational Plan

**Table 4. Laboratory Scheme**

Lab Test	Baseline	Procedure		Discharge	30 days, & 1 Year
		Pre	Post		
Complete Blood Count 
 
White Blood Cell Count
 
Red Blood Cell Count
 
Hemoglobin
 
Hematocrit
 
	X			X	
Platelet count	X			X	
Urea and Creatinine	X	X*	X**	X	X
BNP or ProBNP	X			X	X
INR (if subject is on Coumadin/Warfarin)	X				
Troponin or CK, CK-MB	X				
Albumin	X				X

\* Within 72 hours before index procedure

\*\*Within 48 hours after index procedure

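### Periprocedural myocardial infarction needs a post-procedure cardiac marker that the laboratory schedule never requires, so its classification rests on unscheduled testing at each site

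*Combined protocol and SAP*

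**What the plan says.** Table 2 in Section 5.4 makes the appendix operative: "Adverse events will be documented according to definitions in Appendix D".

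Appendix D then sets two limbs for a periprocedural infarction, joined by AND. The clinical limb is "New ischemic symptoms (eg, chest pain or shortness of breath), or new ischemic signs". The laboratory limb is "Elevated cardiac biomarkers within 72 h after the index procedure consisting of at least 1 sample postprocedure", with a peak above 15 times the upper reference limit for troponin or 5 times for CK-MB. Where the baseline marker was already raised, "a further increase of at least 50% postprocedure is required AND the peak value must exceed the previously stated limit".

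On sampling, Table 2 says "Blood lab tests will be collected at each required interval" and refers to Table 4 for the tests. The Table 4 row "Troponin or CK, CK-MB" carries one mark, under Baseline. Section 5.7.3 gives the post-procedure draw as "Blood work (within 48 hours post implant, refer to Table 4", followed by creatinine and urea. Section 5.7.1 lists the same two analytes before the procedure.

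**The concern.** The plan collects the baseline half of a before-and-after comparison and leaves the other half to chance. Acute myocardial infarction is on the list of anticipated adverse events in Section 8.2. Section 9.2 makes all serious adverse events, and all non-serious cardiovascular ones, reportable. Suspected infarctions will therefore be reported, and the Appendix D definition will have to be applied to them.

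Where a subject has ischemic signs and no marker was drawn, the laboratory limb is missing rather than negative, and the event can be neither confirmed nor ruled out under the definition. How often that happens depends on local testing practice. Section 4.2 allows up to 12 sites. Section 5.7 describes a cardiac surgeon performing the transaortic procedure and an interventional cardiologist the subclavian/axillary one, so testing habits could differ by arm as well as by site; that last step is inference, not something the documents state. Section 6.5 has each route analysed separately for its own CE Mark report, and Section 4.2 allows data from other trials to be added. Uneven ascertainment would make infarction counts harder to compare in both settings.

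**Working it through.** No sample-size, power or error-rate figure is involved, and the plan states no number for MI to reproduce. The check compares the definition with the schedule.

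**1. What the definition needs (Appendix D).** At least 1 cardiac marker sample after the procedure and within 72 hours. If the baseline value was raised, the two values must be compared, with a further rise of at least 50%.

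**2. What the schedule supplies for troponin or CK/CK-MB.**

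| Time point | Table 4 | Text list |
|---|---|---|
| Baseline | scheduled | Section 5.6: blood work, tests not itemised |
| Before procedure (within 72 h) | none | Section 5.7.1: urea, creatinine |
| After procedure (within 48 h) | none | Section 5.7.3: creatinine, urea |
| Discharge | none | Section 5.8.1: blood work, tests not itemised |
| 30 days and 1 year | none | Sections 5.8.2 and 5.8.4: blood work, tests not itemised |

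The text lists in 5.7.1 and 5.7.3 agree with Table 4, so the gap is not an artefact of how the table was extracted.

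**3. Count.** Scheduled post-procedure samples that could meet the criterion: 0 per subject. Needed: at least 1. With the planned minimum of 45 subjects in each of two arms, 2 × 45 = 90 subjects have no scheduled sample of this kind.

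**4. Is it likely to be deliberate?** Two other Appendix D events have measurements that match their definitions. Acute kidney injury uses creatinine change up to 48 hours, and creatinine is drawn within 48 hours (5.7.3). Disabling stroke uses the modified Rankin score at 90 days, and Section 5.9 schedules that assessment 90 days after a neurological event. MI has no such match, which suggests an oversight.

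**5. Choice of marker.** Table 4 permits troponin or CK with CK-MB and does not say that a later sample should use the same one. Appendix D gives thresholds for troponin and CK-MB only. Total CK has none, so it cannot satisfy the laboratory limb.

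**6. Where the definition feeds in.** MI is not in the primary endpoint (6.2.1), the secondary endpoints (4.3.2, 6.2.2) or the endpoint events listed in Section 9.2. In cardiovascular mortality it appears only as one example of a cardiac cause. That definition separately counts procedure-related deaths, sudden or unwitnessed deaths and deaths of unknown cause, so it does not turn on the marker.

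**7. Scale.** One event in a 45-subject arm is 1/45 = 2.2 percentage points. This is only the weight of a single event. The documents give no expected MI rate and no rate of local testing, so the number missed cannot be estimated.

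**The case against.** The strongest reply is that a routine assay alone never makes an infarction under this definition. The marker matters only in a subject with ischemic symptoms or signs, and there the site may test clinically. Section 8.2 leaves care of adverse events to the site's standard. Section 9.2 requires serious and cardiovascular events to be reported, has records of the later medical course submitted as applicable, and lets the sponsor ask for more information. This stands. A reader might infer that the study can never establish a periprocedural infarction; the documents do not support that.

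A reader might also infer that infarctions will be missed because anaesthesia masks symptoms. The documents do not state the type of anaesthesia; Section 5.7 lists only an anesthesiologist. Appendix D also accepts signs in place of symptoms, and the plan provides rhythm monitoring and imaging during the procedure (5.7.2) and an ECG and echocardiogram at discharge (5.8.1).

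Nor can it be said that the baseline marker serves no purpose. It is the comparator whenever a clinical sample is drawn, and it may bear on the exclusion for MI within the previous 30 days.

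Finally, Section 6 specifies no analysis of MI, and the events committee charter and case report forms are held separately and may address work-up of suspected events. That limits the consequence. It does not supply the missing sample: nothing in the plan requires a clinically driven marker, fixes its timing, or says how an event without one is to be classified.

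**Conclusion.** The mismatch is real and of limited impact. No sample scheduled by the plan can meet the laboratory limb of the periprocedural MI definition, so classification depends entirely on unscheduled, clinically driven testing. Subjects with ischemic signs and no marker cannot be classified, and detection may be uneven across sites and between the two arms.

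The effect stays within adverse event documentation and safety reporting. The primary endpoint, the secondary endpoints and cardiovascular mortality do not depend on it. A reader might conclude that a report of no infarctions would carry no information. That goes too far, since suspected events must still be reported; such a count would be weaker evidence than it appears. Under-detection is possible, but its size is unknown.

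The conclusion assumes that Table 4 with Sections 5.7.1 and 5.7.3 is the full laboratory schedule, and that the separately held charter and case report forms add no mandatory marker.

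**What to change.** In Table 4 and Section 5.7.3, add the cardiac marker measured at baseline to the existing draw within 48 hours after implant, which falls inside the 72-hour window. Specify troponin or CK-MB, and require the same marker for both samples in a given subject. Total CK should not stand as the only marker, because the definition has no threshold for it.

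The cost is one extra assay per subject, about 90 in all (2 × 45), possibly a little more blood at a draw already planned, and edits to one table and one list. No visit is added. One limitation remains: a single draw may miss the peak to which the definition refers, so a value below the threshold would not fully exclude an infarction.

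If the sponsor prefers not to add the assay, one sentence would reconcile the sections: periprocedural MI is ascertained only from clinically driven samples, and its count in each arm is to be read accordingly.

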## Clinical Investigational Plan

### 1. Definitions:

- a. **Stroke:** Stroke is an acute symptomatic episode of neurological dysfunction attributed to a vascular cause.

#### Subclassifications of stroke:

Ischemic Stroke is defined as an acute symptomatic episode of focal cerebral, spinal, or retinal dysfunction caused by an infarction of central nervous system tissue.

Hemorrhagic Stroke is defined as an acute symptomatic episode of focal or global cerebral or spinal dysfunction caused by a nontraumatic intraparenchymal, intraventricular, or subarachnoid hemorrhage.

#### Stroke Disability (consistent with VARC2 Definitions):

#### Severity

- i. **Disabling (Major):** an mRS score of 2 or more at 90 days and an increase of at least 1 mRS category from an individual's prestroke baseline
  - ii. **Non-disabling (Minor):** an mRS score of <2 at 90 days or 1 that does not result in an increase of at least 1 mRS category from an individual's prestroke baseline
- b. **Cerebral Infarction:** Evidence of brain cell death from imaging studies or pathological examination. If there are clinical symptoms, then it is a stroke; otherwise, it is an asymptomatic cerebral infarction.
- c. **Transient Ischemic Attack (TIA):** A transient (less than 24 hrs) episode of neurological dysfunction caused by focal brain, spinal cord, or retinal ischemia, without acute infarction. No evidence of infarction if imaging performed.
- d. **Encephalopathy:** Altered mental state (e.g., seizures, delirium, confusion, hallucinations, dementia, coma, psychiatric episode).
- e. **Intracranial Hemorrhage:** Collection of blood between the brain and skull. Subcategorized as epidural, subdural, and subarachnoid bleeds.

### **Bleeding (VARC2)**

#### **Life-threatening or disabling bleeding**

- Fatal bleeding (BARC type 5) **OR**
- Bleeding in a critical organ, such as intracranial, intraspinal, intraocular, or pericardial necessitating pericardiocentesis, or intramuscular with compartment syndrome (BARC type 3b and 3c) **OR**
- Bleeding causing hypovolemic shock or severe hypotension requiring vasopressors or surgery (BARC type 3b) **OR**
- Overt source of bleeding with drop in hemoglobin of greater than or equal to 5 g/dL or whole blood or packed red blood cells (RBCs) transfusion greater than or equal to 4 U (BARC type 3b). *Given 1 U of packed RBC typically will raise blood hemoglobin concentration by 1 g/dL, an estimated decrease in hemoglobin will be calculated.*

#### **Major bleeding (BARC type 3a)**

- Overt bleeding either associated with a drop in the hemoglobin level of at least 3.0 g/dL or requiring transfusion of 2 or 3 units of whole blood/RBC, or causing

## Clinical Investigational Plan

	
hospitalization or permanent injury, or requiring surgery AND
 
 
Does not meet criteria of life-threatening or disabling bleeding
 
 
Minor bleeding (BARC type 2 or 3a, depending on the severity)
 
 
Any bleeding worthy of clinical mention (eg, access site hematoma) that does not qualify as life-threatening, disabling, or major
 

Acute Kidney Injury (AKIN Classification)
 
(VARC2)
	
Change in serum creatinine (up to 48 h) compared with baseline
 
Stage 1
 
Increase in serum creatinine to 150% to 199% (1.5 to 1.99 X increase compared with baseline) or increase of greater than or equal to 0.3 mg/dL (26.4 mmol/L) or Urine output <0.5 mL/kg per hour for >6 but <12 hours
 
Stage 2
 
Increase in serum creatinine to 200% to 299% (2.0 to 2.99 X increase compared with baseline) or Urine output <0.5 mL/kg per hour for >12 but <24 hours
 
Stage 3
 
Increase in serum creatinine to greater than or equal to 300% (3 X increase compared with baseline) or serum creatinine of <math>\geq 4.0</math> mg/dL (354 mmol/L) with an acute increase of at least 0.5 mg/dL (44 mmol/L) or Urine output <0.3 mL/kg per hour for <math>\geq 24</math> hours or anuria for <math>\geq 12</math> hours. Patients receiving renal replacement therapy are considered to meet Stage 3 criteria irrespective of other criteria.


Vascular Access Site and Access-Related Complications (VARC2)
	
Major vascular complications
 
 
Any aortic dissection, aortic rupture, annulus rupture, left ventricle perforation, or new apical aneurysm/pseudo-aneurysm or
 
Access site or access-related vascular injury (dissection, stenosis, perforation, rupture, arteriovenous fistula, pseudoaneurysm, hematoma, irreversible nerve injury, compartment syndrome, percutaneous closure device failure) leading to death, life-threatening or major bleeding*, visceral ischaemia or neurological impairment or
 
Distal embolization (non-cerebral) from a vascular source requiring surgery or resulting in amputation or irreversible end-organ damage or
 
The use of unplanned endovascular or surgical intervention associated with death, major bleeding, visceral ischaemia or neurological impairment or
 
Any new ipsilateral lower extremity ischemia documented by patient symptoms, physical exam, and/or decreased or absent blood flow on lower extremity angiogram or
 
Surgery for access site-related nerve injury or
 
Permanent access site-related nerve injury
 
 
Minor vascular complications
 
 
Access site or access-related vascular injury (dissection, stenosis, perforation, rupture, arteriovenous fistula, pseudoaneurysms, hematomas, percutaneous closure device failure) not leading to death, life-threatening or major bleeding*, visceral ischaemia or neurological impairment or
 

## Clinical Investigational Plan

- Distal embolization treated with embolectomy and/or thrombectomy and not resulting in amputation or irreversible end-organ damage or
- Any unplanned endovascular stenting or unplanned surgical intervention not meeting the criteria for a major vascular complication or
- Vascular repair or the need for vascular repair (via surgery, ultrasound-guided compression, transcatheter embolization, or stent-graft) or

### Percutaneous closure device failure

Failure of a closure device to achieve haemostasis at the arteriotomy site leading to alternative treatment (other than manual compression or adjunctive endovascular ballooning)

### Acute Device Success (VARC)

Acute device success is defined as a subject who achieves a) successful vascular access, delivery and deployment of the device and successful retrieval of the delivery system, b) correct position of the device in the proper anatomical location, c) intended performance of the prosthetic heart valve, and d) only 1 valve implanted in the proper anatomical location.

Device success is a 'technical' composite endpoint meant to characterize the acute device and procedural factors which underlie vascular access, delivery, and performance of the TAVI system. Echocardiography should be routinely utilized as the standard for measuring prosthetic valve stenosis and regurgitation immediately after TAVI, and should always be performed in a resting state, either within 24–48 h after the index procedure or before hospital discharge.

Prosthetic Valve Stenosis Criteria In conditions of normal or near normal stroke volume (50–70 ml). (VARC2)	Parameter	Normal	Mild Stenosis	Moderate/severe Stenosis
	Peak velocity (m/s)	less than 3	3–4	greater than 4
	Mean gradient (mm Hg)	less than 20	20–40	greater than 40
	Doppler velocity index	greater than or equal to 0.35	0.35–0.25	less than 0.25
	Effective orifice area (cm  )	greater than 1.1*	1.1–0.8	less than 0.80
Prosthetic Valve Regurgitation Criteria (Central and Paravalvular)	Parameter	Mild	Moderate	Severe
	Valve structure and motion	Usually normal	Usually abnormal	Usually abnormal
	Left ventricular size	Normal	Normal/mildly dilated	Dilated
	Doppler parameters ( qualitative or semiquantitative )			

\* Effective orifice area (EOA) used in this protocol is 1.0 cm^2 for Portico valve of 23 mm diameter.

